
Intervention Protocol:

After participants complete the interviews, and chronic fatigue patients complete the collection of saliva and blood, they will open an envelope that will advise them of the group they were randomly assigned to (PP-T-CBSM or T-HI). Participants who live outside our catchment area will be contacted to inform them of their randomization group. Randomization will occur in waves of eight, four dyads will be randomized to PP-T-CBSM and 4 to P-HI). Subjects randomized to PP-T-CBSM will receive 10 weeks of group intervention as described herein. A total of 4 dyads (CFS patient and their identified partner) will meet once weekly by videophone for approximately a one hour session at a mutually convenient set time. The content of the PP-T-CBSM protocol will comprise two broad domains: Cognitive, behavioral and interpersonal skills training and relaxation/imagery. The Cognitive, Behavioral and Interpersonal skills component presents information concerning stressors and stress responses from a biopsychosocial perspective. The initial 5 weeks emphasize: (1) the importance of appraisals in the stress response and in symptom occurrence; (2) understanding automatic thoughts and cognitive distortions; (3) identifying and monitoring automatic thoughts; (4) disputing and restructuring cognitive distortions into more rational thoughts, and (5) learning adaptive problem-focused and emotion-focused coping skills. By monitoring automatic thoughts associated with negative emotions, participants increase their awareness of cognitive appraisals that precede changes in emotion. Stressors of primary importance in this study are those concerning the physical symptoms of CFS and the losses associated with the illness. Participants learn how automatic thoughts, including cognitive distortions may contribute to symptom magnification and ensuing feelings of loss of perceived control. The remaining 5 weeks focus on

strategies to improve interpersonal communication, self-esteem, and quality of life, and to encourage appropriate emotional expression and assertion skills. During the sessions individual problems are addressed and homework is reviewed. Based on our experience, the combination of social support and self-reinforcement seems to increase participants' use of these strategies and foster self-efficacy, self-esteem, and a sense of perceived personal control. The Relaxation/Imagery component includes targeting anxiety reduction through training in deep muscle relaxation. Participants use imagery of muscle groups rather than progressive muscle relaxation (tensing and relaxing muscle groups) because in our previous clinical work, we have found that tensing of muscle groups often increases joint and muscle pain-related symptoms that many CFS patients experience. In addition to reducing anxiety, relaxation training has been helpful for many of our participants in overcoming sleep problems associated with CFS. Autogenics, guided imagery, deep breathing and meditative techniques are taught in later weeks. We found that some members tend to learn and acquire skills better when presented in a didactic form while others may assimilate information better if it is introduced through images and metaphors. All sessions begin with a brief review of the previous meeting. The lively interactive format of our sessions enhances understanding and retention of the intervention materials through active participation. This multimodal/interactive approach should maximize the effectiveness of PP-T-CBSM in teaching stress reduction strategies simultaneously to patients and partners. Participants also receive a Participant Workbook, which contains a summary of the rationale for each module, outlines of each technique taught, and homework exercises and self-monitoring sheets to be completed by patient and partner. Finally, key points of all PP-T-CBSM strategies are available in text, audio and/or video form through pull-down screens in our Telecare system, which participants can access at any time. The video telephone is menu driven and has tri-modal output (text, speech, video).

Subjects randomized to Telephone Health Information (T-HI) condition will receive 10 weeks of individual telephone sessions of approximately one hour. This control condition is designed to provide equal amounts of attention and contact time without any active treatment (CBSM) being given. T-HI is designed to control for common factors such as attention, supportiveness, empathy and enthusiasm. Social support processes (e.g., group cohesiveness) are an "active ingredient" in the T-CBSM intervention and social support changes will be tested as part of our hypothesized model. By providing T-HI in an individual format, we are controlling for facilitator's time and attention, supportiveness, and empathy, but we retain the ability to test whether a supportive group intervention facilitates better quality of life and health outcomes. If we were to provide T-HI in a group format, we would be equalizing the groups on a factor that we are actually aiming to test. Moreover, once a group is assembled, it is very difficult to deter social processes as they may occur within the group or as part of ancillary group contact. The sessions cover the benefits of titrated physical and leisure activity, sleep, and proper nutrition (e.g., balanced diet, nutrition guidelines for adults), and the importance of receiving regular medical care and follow-up. Participants will be encouraged to ask questions and to discuss material at a personalized level to increase its relevance (e.g., asked to complete dietary log to increase awareness of eating habits; monitor physical activities; etc.). The material presented will be comprised of information that is commonly available and is designed to complement the ongoing medical care that participants receive from their medical treatment provider(s). Each session consists of a didactic presentation of the topics and activities to promote discussion. Patients report that they find the material to be useful. Participants will receive a Participant Workbook, which contains a summary of the information presented in each individual session and health resources. In addition, participants will be encouraged to inform their provider(s) about their study participation and to consult with provider(s) before initiating any health behavior changes (e.g., increasing physical activity). In addition to printed materials, participants will have access to system with recorded T-HI information. Usage of the system will be monitored as an indicator of dose.

Treatment fidelity will be monitored by audio taping a random sample of the intervention sessions. Participants will be asked for their permission to be audio taped at the end of the consent form. If participants do not feel comfortable being audio taped this will not affect their participation in the study. Those participants refusing to be audio taped will not be audio-taped at any point of the intervention. In addition audio tapes will be destroyed upon participant's request.

Follow-up Interview Protocol:

Upon completion of the 10 week program for both PP-T-CBSM and T-HI, participants will be contacted by a study staff member to coordinate the 5 (approximate) month follow-up interview. Participants will be sent their interview via email to complete electronically using SurveyMonkey. They will also be mailed a saliva kit with instruction on how to complete it. Participants will have a 2-3 week window to complete the interview and saliva collection before scheduling a blood draw at one of our lab locations. Participants who live outside our catchment area will follow the same lab collection protocol outlined above. This procedure will be repeated in four months when the last collection point at about the 9 month follow-up.

Blood Draw Protocol:

Chronic fatigue patients will be asked to provide about 2 ounces of blood at each time point. The blood collection will be conducted at one of the designated lab locations. An appointment will be made by one of our staff members who will also be meeting the participant at the lab location. No identifying patient information will be shared with the lab sites; appointments will be made using the study name and subject ID and pre-printed labels with subject's ID will be used on collected blood samples. A member of the study staff will be with the participant at all times to insure that the blood collection is conducted safely. The saliva samples and blood sample will be taken to [name] Lab (E. M. Papper Laboratory of Clinical Immunology). Participants who live outside our catchment area will be asked to visit one of our contracted lab (for example Labcorp) in their area. Participants will be sent a package with detail information about the blood draw protocol (including lab request forms, tubes and instructions to the lab) and how to send back the samples to [name] Lab.

Technical Support and Installation of the VideoPhone System:

Participants will receive a VideoPhone System as part of their study program and will be asked to return the system after completing the study. The VideoPhone system will be installed either by one of our technical staff member (if participant lives within our catchment area) or we will send those participants who live outside our catchment area detail instructions on how to install the system (a detailed email with a demonstration installation video link). In addition our technical support team will contact each participant to check that that system is working properly. Each participant will also receive instructions on how to use the different features of the system either in person at the installation appointment or via email by sending participants a video with details instructions. The therapist assigned to work with the dyad will contact them to make sure they understand how to use the VideoHealth system and answer any questions regarding the features and use of the system.

- 4.4.A. **Standard Measures:** Click the "Add" button to open the search window, then click the "Find" button to browse and select measures.

Name of Measure	Brief Description	Type of Measure
There are no items to display		

NOTE: A copy of the first page of each standard measure is provided in the [Library of Standard Measures](#) for verification. Ensure that the version being used in this study is the same as the version that has been selected.

Upload any questionnaires and/or assessment tools to be used that are not listed above:

Name	Description	Version
CFS Core Battery-CFS		0.01
CFS Core Battery-Partner		0.01
CFS Patient Project Evaluation 4-16-12		0.01
CFS Screening Form 9-20-10		0.02
Partner Project Evaluation 4-16-12		0.01
Short Version of PT follow up interviews Apr2013		0.01
TICS Telephone Interview for Cognitive Status Form		0.01
VideoHealth CFS Patient Assessment Surveymonkey 6-3-11		0.01
VideoHealth Partner Assessment Surveymonkey 6-3-11		0.01
VideoHealth Screening Rev-Clean 4-1-13		0.01
VideoHealth Study Assessment (CFS) Track Changes 6-3-11		0.01

4.5. Identify and distinguish between those procedures that are standard treatment versus those that are experimental/research-specific.

Not applicable

The use of CBST techniques (e.g. relaxation) in the experimental condition is not part of the standard care for CFS. Beyond these techniques patients in each study condition will be receiving standard of care. Research-specific techniques include things such as relaxation training, cognitive behavioral therapy and group support. Standard treatment for CFS includes but is not limited to medications designed to reduce symptoms. The experimental procedure in this study will not involve medications.

4.6. Describe any therapeutic alternatives that may exist for the study population.

Not applicable

Medication to diminish symptoms and exercise intervention designed to prevent de-conditioning.

4b. Description of Study (cont'd)

Risk/Benefit Assessment

4.7. * Describe the nature, degree, and if available, expected frequency of all potential economic/financial, legal, physical, psychological, social or other risks to which research participants may be exposed as a result of their participation in this research. If applicable, please describe the risk of investigational agents or devices (side effects).

Participants will incur no appreciable physical risks through participation in this study, though they may undergo psychological discomfort at some time points. During the psychosocial intervention, participants will be given specific CFS-related information, as well as be asked to participate in assessment of sensitive topics that may lead some to experience transient and mild anxiety. In addition, some participants are likely to manifest symptom increases from time to time throughout the longitudinal component of the study, and some may experience affective distress. In these cases, every attempt will be made to provide relief and to ameliorate the source of the discomfort. Should participants experience extreme acute or persisting affective reactions at any point during the study period, they will be referred to a psychiatrist or clinical psychologist associated with the site for care. In the event that a participant reports symptoms or concerns of extreme distress (e.g., severe symptoms of depression and/or anxiety suggesting clinical concerns, suicidality, etc.), our interventionists will directly target such symptoms and assess the severity of such distress within the group context while maintaining the group process and eliciting support from other participants. Subsequent to the intervention session, the participant will be contacted individually by one of the interventionists for a more comprehensive assessment of distress. If it is determined at that point that the participant needs individual care, our interventionists and research staff will

be prepared to refer the patient to a source of clinical intervention other than our PP-T-CBSM intervention (a list of referrals will be available). Similarly, should participants experience extreme, acute or persisting affective reactions at any other point during the study period (e.g., assessment, individual contact), they will be referred to the appropriate channels within the UM Department of Psychiatry or Psychology, as well as to a list of community resources/catchment sites in the South Florida area prepared to deliver resources to deal with extreme distress. Similar procedures will be followed for participants in our T-HI condition. The information obtained in this project will help in the development of strategies for promoting quality of life among individuals living with CFS. All participants will receive fair compensation for the time they invest in completing the research protocol.

Participants will also be required to provide blood samples at each time point. Blood samples (about 2 ounces at each of the measurement points) will be taken from a vein in their arm using a needle and blood tube (venipuncture). This will be done by a trained nurse or phlebotomist. Participants may experience discomfort during blood sampling. The risks of blood sampling by venipuncture include the occurrence of a bruise at the site of the needle puncture and, in rare cases, infection or the formation of a small blood clot, swelling of the vein and surrounding tissue, bleeding at the needle puncture site, and fainting. In the event that a subject experiences an injury due to these procedures, medical treatment will be made available through the investigators and staff. The participants will be encouraged to contact the study investigators and staff should they have any questions or concerns at that point in time.

4.8. * Are there potential direct benefits of this research to the subjects?

☒ **Yes** ☐ **No**

4.8.A. If yes, provide a description of the potential direct benefits and indicate if all, or only some, of the subject groups may derive this potential benefit.

It is anticipated that participants will experience more benefits than risks as a result of their participation in the study. In particular we anticipate that the those participants in the intervention condition (PP-T-CBSM) will experience a decrease in illness burden, perceived stress, and distress relative to participating in the attention control group (T-HI condition).

4.9. * Are there potential benefits of this research to society?

☒ **Yes** ☐ **No**

4.9.A. * Please explain:

Helping CFS patients to function better may help them return to employment, and increase their ability to fulfill other responsibilities within their family. The results of this study may provide scientific contributions to society by providing additional insight about the effects of home-based telephone-delivered stress management intervention among other chronic illness and hard-to-reach populations who might benefit from these techniques.

4.10. * Explain why the risk/benefit ratio supports conducting this research.

The investigators believe that this study possesses no greater than minimal risk and that the benefits to the individual and society are greater than its risk.

4c. Description of Study (cont'd)

Data

4.11. *** Describe follow-up, data storage methods, data security, authorized access to records and record retention, including site name and address.**

Participant will have a total of 3 assessment time points, at the beginning of the study, and at approximately 5- and 9-month follow-ups. The participants will also be asked to provide samples of their saliva and blood at each time point. The screening forms, assessments, and consent forms will be safely stored at the Center on Aging ([name]) under double lock and key. Electronic information of the data will also be safely secured using access privileges and passwords. Saliva and blood samples will be stored in [name] lab in the E.M Papper Clinical Immunology Lab, Rosenstiel 8th Floor. Only study related personnel will have access to the participant's files.

4.12. *** Support the study validity by describing the statistical design, including quantitative and qualitative methods used to analyze data.**

The study is a 2 (experimental, control group) X 3 (pre-intervention, post-intervention, follow-up) randomized controlled design that will test the effects of a PP-T-CBSM intervention on hypothesized psychological, physiological and clinical/physical health indicators in a sample of patients diagnosed with CFS. Psychological data is derived from valid and reliable interview and questionnaire methods based upon published psychometric studies. Physiological data is derived from bioassays of collected biological specimens (blood, saliva) using standardized methods for quantitating concentrations of hormones and cytokines. The primary outcome is CFS physical symptoms and secondary outcomes include indicators of psychological and physiological functioning hypothesized to mediate the effects of the intervention on physical symptoms. Study hypotheses are tested using multivariate repeated measures statistical procedures designed to test for differences in the changes in study outcomes over time as a function of random assignment to study groups. Statistical controls (covariates) are employed where appropriate. All analyses have been guided by underlying theory and the study sample size was determined by power analyses based upon prior published work and pilot studies.

Privacy/Confidentiality Agreements

4.13. **Describe any privacy agreements or certificates of confidentiality, if applicable.**

Participants will be provided with a copy of the consent form as part of their initial interview or telephone contact. The consent form outlines the study's protocol and guidelines regarding confidentiality. In addition the assessor will review each section of the consent form, including the section about confidentiality.

4d. Description of Study (cont'd)

Deception

4.14. *** Is the use of deception part of the study design?**

☐ Yes ☒ No

If yes, please answer the following 3 questions:

4.14.A. **Describe in detail the nature of the deception and explain why this is necessary for the research.**

4.14.B. **State how, when, and by whom the research subjects will be debriefed.**

4.14.C. **Upload a copy of the debriefing script.**

5. Study Participants

Per 45 CFR 46, human subjects (participants) means a living individual about whom an investigator (whether professional or student) conducting research obtains:

1. data through intervention or interaction with the individual; or
2. identifiable private information (i.e. pathological specimens, medical records, etc.)

5.1. * Participant Age:

Check all that apply	Notes
 0-6	Parent Permission/Consent required for each participant
 7-17	Parent Permission/Consent & Child Assent required for each participant
 18-65	Consent required for each participant unless a waiver of consent is approved by the IRB
 65+	Consent required for each participant unless a waiver of consent is approved by the IRB

**5.2. For the following questions, please use integers for your responses. For any question that is not applicable, please enter the number 0.
(Do not enter commas, decimal points or special characters)**

5.2.A. * Maximum number of subjects in the Protocol to be *screened* at all sites (regardless of PI):
600

5.2.B. * Total number of subjects in the Protocol to be *studied* at all sites (regardless of PI):
300

University of Miami

5.2.C. * Maximum number of subjects to be *screened* by this PI at *UM*:
600

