Hypoth 1.1 CFS patients assigned to PP-T-CBSM will show greater reductions in average CDC-based Symptom Frequency and Duration compared at 5- and 9-month follow-up vs. those in T-HI.

Hypoth 1.2 CFS patients assigned to PP-T-CBSM will show decreases in CFS symptoms of diarrhea, fatigue, muscle pain, unrefreshing sleep, sinus problems and general weakness, at 5- and 9-month follow-up vs. those assigned to T-HI.

SECONDARY AIMS

AIM 2: To determine if T-CBSM intervention improves di-urnal cortisol regulation and immune regulation (pro-inflammatory:anti-inflammatory cytokine ratio ([IL-1B+ IL-6 + TNF-x]:[IL-13 + IL-10]) relative to participants in the T-HI condition and how these changes relate to CFS symptoms.

Hypoth 2.1. CFS patients assigned to PP-T-CBSM will show greater reductions in pro-inflammatory: anti-inflammatory cytokine level ratio at 5- and 9-month follow-up compared to those assigned to T-HI.

Hypoth 2.2. CFS patients assigned to PP-T-CBSM will show greater increases in the AM-PM negative slope of salivary cortisol at 5- and 9-month follow-up compared to those assigned to T-HI.

Hypoth 2.3. The magnitude of reductions in CFS symptom frequency and severity from baseline

to 9 month follow-up will be associated with greater reductions in the pro-inflammatory: anti-inflammatory cytokine ratio and greater increases in the AM-PM salivary cortisol negative slope.

AIM 3: To test whether reductions in total and specific CFS symptoms and neuroimmune process indicators in PP-T-CBSM are associated with greater improvements in patient/partner psychosocial functioning (decreased stress, depression and social disruption and increased social support).

Hypothesis 3.1 Patients/partners assigned to PP-T-CBSM will show greater reductions in stress, depression and social disruption, and greater increases in social support at 5- and 9-month follow-up compared to those assigned to T-HI.

Hypothesis 3.2 The magnitude of reductions in CFS symptoms and pro-inflammatory cytokines and increases in the AM-PM salivary cortisol slope from baseline to 9 month follow-up are associated with greater decreases in stress, depression and social disruption and greater increases in social support.

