models in CFS, though drop-out rates range up to 42% (52). Group-based CBT combined with body awareness and exercise training has also been shown to be effective for CFS in recent work (53). In line with our stress model of CFS symptom exacerbation, our work has focused on testing group-based cognitive behavioral stress management (CBSM) intervention which is designed to reduce stress through relaxation, and depression by modifying participants' outlook and cognitive appraisals through CBT, teaching adaptive coping strategies and interpersonal skills such as assertiveness and anger management, and when conducted in a group format may also improve their perceptions of social support (54). Group-based CBSM improves mood and quality of life, modulates cortisol output, improves cellular immune functioning and decreases signs of herpesvirus reactivation among populations suffering from other immunomodulating illnesses or treatments (55- 60). Our conceptual model specifies the ways in which psychological distress, HPA axis functioning and immunologic abnormalities may act as mediators of stress-related exacerbation and/or maintenance of CFS physical symptoms (37). We hypothesize that CBSM affects symptoms through these mediators as well. Stress is experienced not only by the CFS patient but is likely to be also experienced by partners or family members who must make lifestyle adaptations to the patients illness—a well-established phenomenon in family members and caregivers of persons with chronic illness (61). Members of our team have argued for the importance of involving family members in psychosocial interventions for persons dealing with chronic illness (61). In prior work we showed that a patient-caregiver dual target psychosocial intervention improved depression and health symptoms in spinal cord injury patients when compared to either an inert control condition or a patient-focused intervention (62). We reasoned that a CBSM package—designed to reduce psychological stress (relaxation), alter cognitive appraisal aspects of CFS (via CBT), and teach interpersonal skills (assertiveness)—if taught simultaneously to CFS patients and their partners, may be effective in interrupting the biobehavioral mechanism maintaining or exacerbating some of the symptoms of CFS. This intervention may impact physical status and neuroimmune processes by way of stress/depression reduction, reduced social disruption, and improved social support. We propose that CBSM may affect CFS physical symptoms by first modulating a set of CBSM targets. Changes in these intervention targets are hypothesized to improve physical symptoms by improving psychosocial functioning and then reducing distress-related HPA axis dysregulation and modulating immune indicators.

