Rationale and Methodology

- 4.4. *** In non-technical, lay language, describe the study design and all study procedures, in order of sequence and timing. Include length of subject participation, what tasks are involved in the study, what tests or procedures subjects will be asked to complete or undergo, specific measures to be used, etc. If applicable, include frequency of visits, duration of visits, and study procedure calendar.**

Study Design:

This is a randomized controlled trial testing the effects of patient-partner based dual focused videotelephone-delivered CBSM (PP-T-CBSM) vs. a patient-partner attention-time matched health information control (T-HI). This study has a 2 X 3 (group: PP-T-CBSM, T-HI) X time (pre-intervention, about 5mo post, about 9 mo post) design with the primary outcome variable being total CDC-based CFS symptoms (frequency and severity). In addition we will explore selected individual symptoms to evaluate whether the intervention's overall effects are largely accounted for by specific symptom changes. The secondary outcome variable is a composite measure of pro-inflammatory cytokines: anti-inflammatory cytokines measured as the ratio of [IL-1B + IL-6 + TNF-x]: [IL-10 + IL-13]. The other secondary outcome variable is the AM-PM slope of salivary cortisol output over a 48hr sampling window (SP). We hypothesize that patients assigned to PP-T-CBSM will show larger decreases in CFS symptoms vs. those assigned to T-HI. We are also hypothesizing the greatest decrease in the pro-inflammatory: anti-inflammatory cytokine ratio and greatest increase in AM-PM negative SP in patients assigned to PP-T-CBSM vs. T-HI. We will examine whether changes in cytokines and cortisol are associated with psychosocial functioning to explain the effects of PP-T-CBSM on CFS symptoms. All analyses will control for medications, physical activity, and possible confounders per preliminary analyses. A total of 150 CFS patients and their partners between the age of 21 and 75 will be recruited for this study, with an anticipated retention of 124 at final assessment time point T3.

Study Procedures:

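### The mechanism hypotheses state only associations of change to 9 months, while the plan speaks of mediators; a time-ordered mediation analysis with an arm term should be added

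*Combined protocol and SAP*

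**What the plan says.** **The hypotheses (opening summary, Secondary Aims).** Hypoth 2.3 begins "The magnitude of reductions in CFS symptom frequency and severity from baseline" and continues "to 9 month follow-up will be associated with greater reductions in the pro-inflammatory: anti-inflammatory cytokine ratio", together with a greater increase in the negative AM-PM cortisol slope. The window is attached to the symptom change; none is written for the cytokine or cortisol change. Hypothesis 3.2 puts on one side "The magnitude of reductions in CFS symptoms and pro-inflammatory cytokines and increases in the AM-PM salivary cortisol slope from baseline to 9 month follow-up" and on the other, with no window, improvements in stress, depression, social disruption and social support.

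**The claims made for them.** Section 4.12 says that "secondary outcomes include indicators of psychological and physiological functioning hypothesized to mediate the effects of the intervention on physical symptoms". Section 4.2, Background, part 5, says "We hypothesize that CBSM affects symptoms through these mediators as well" and gives an order: psychosocial functioning improves, then HPA and immune regulation, and symptoms follow. The Innovation part of 4.2 presents the trial as the first randomized test of a neuroimmune mechanism of this kind. Section 4.4, Study Design, will relate cytokine and cortisol changes to psychosocial functioning "to explain the effects of PP-T-CBSM on CFS symptoms"; the association described there leaves symptoms out.

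**The methods.** Section 4.12 gives multivariate repeated-measures tests of differences in change between randomized groups. No lagged, indirect-effect or mediation model appears. The covariates named in 4.4 are medications, physical activity and confounders found in preliminary analyses; 4.12 adds covariates where appropriate. Arm is not named for the mechanism analyses.

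**The measurements.** Section 4.4 schedules blood, saliva and questionnaires at baseline and at about 5 and 9 months.

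**The concern.** If both sides of each association run from baseline to 9 months, a positive result has at least four explanations: the mediator moved the symptoms; symptoms moved the mediator; something else moved both; or the intervention moved both with no link between them.

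The second is not far-fetched here. The plan's own model (section 4.2, Background, part 2) has patients becoming distressed because of their symptoms, and that distress further disturbing immune function. This is a path from symptoms to biology.

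At stake is the secondary claim that gives the trial much of its stated novelty. The opening summary already reads pilot associations of change as support for the neuroimmune model, so the same reading of the new results is likely unless the plan sets the limits beforehand.

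**Working it through.** The plan states no effect size, SD, alpha or power for these analyses (4.12 mentions a power analysis without inputs), so there is no figure to reproduce.

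**Inputs from the documents.** 150 patients, 75 per arm (opening summary); 124 expected at 9 months (4.4, Study Design); 124/150 = 82.7%.

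**Assumptions.** Two-sided 5% test; equal arms; an arm difference of d within-arm SDs of change on both variables; no within-arm correlation.

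**1. Correlation created by allocation alone.** A 0/1 arm indicator with equal allocation has variance 0.25. The pooled covariance of the two changes is therefore 0.25d² and each pooled variance is 1 + 0.25d², giving r = 0.25d²/(1 + 0.25d²). By Fisher's z, λ = atanh(r) × √(124 − 3) = 11 × atanh(r), and the rejection probability is Φ(λ − 1.96) + Φ(−λ − 1.96).

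| d | 0.25d² | r | λ | Rejection |
|---|---|---|---|---|
| 0.3 | 0.0225 | 0.022 | 0.242 | 5.7% |
| 0.5 | 0.0625 | 0.059 | 0.648 | 9.9% |
| 0.8 | 0.1600 | 0.138 | 1.527 | 33.3% |

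**2. Other explanations, by simulation.** 4,000 runs, 62 per arm, half the variance stable within person, d = 0.5 except in the first row. No path from mediator to symptoms exists, so every rejection is false. Entries are percentages of runs significant at 5%; the slashes follow the values in the first column.

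| Data-generating setting | Pooled same-window change | Same, plus arm | 5-month mediator to 9-month symptoms, with arm and baselines | Same, plus 5-month symptoms |
|---|---|---|---|---|
| Arm moves both, d = 0.3/0.5/0.8 | 6/11/34 | 6/5/5 | 5/5/5 | 5/5/6 |
| 5-month symptoms drive the 9-month mediator, 0.3/0.5 | 64/89 | 36/70 | 5/4 | 5/5 |
| Shared factor at each visit, 0.3/0.5/0.7 | 31/76/99 | 14/61/97 | 5/5/5 | 7/11/15 |
| Persistent common cause, 0.3/0.5/0.7 | 30/76/99 | 15/60/97 | 22/80/100 | 12/37/66 |

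The arm term removes the first problem and none of the others. When a true path of 0.3 from the 5-month mediator to 9-month symptoms is simulated instead, the pooled same-window test is significant in 64% of runs, the same as for a reverse path of 0.3. It cannot tell the two directions apart.

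**3. What the time-ordered model can find.** With a true lagged path of 0.2, 0.3 or 0.4 and d = 0.5, both links (arm to mediator, and mediator to symptoms adjusted for 5-month symptoms) are significant in 56%, 82% and 88% of runs.

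**4. Where it fails.** Treatment lasts 10 weeks, and the pilot (4.2, Study 3) reports cytokine and symptom changes both present by 5 months. If mediation is complete by then, 5-month symptoms lie on the pathway and adjusting for them removes it. Simulated with a path of 0.3 to 0.7 completed by 5 months, the adjusted model rejects in 4% to 6% of runs with error-free measures. With noisy measures it rejects in 9% to 21%, against 13% to 42% without the adjustment. The gap depends on the assumed noise; its direction does not.

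**The case against.** The hypotheses say associated, not mediated. Section 4.12 says only that mediation is hypothesized, and the Innovation part of 4.2 claims evidence stronger than an observational study would give, not proof. That is fair to the two hypotheses; it does not supply the analysis that the mediator language calls for.

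A reader might infer that the plan uses simple correlations with no adjustment for arm. The documents do not say so. They give hypotheses without models, and the covariate clauses in 4.4 and 4.12 could admit arm. Aim 3, the parent of Hypothesis 3.2, speaks of reductions in the PP-T-CBSM arm; on a within-arm reading the allocation-induced correlation is zero. The identical window on both sides is likewise the natural reading, not the written one. These points stand: the gap is that model, sample and windows are unstated.

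The allocation effect is also the weakest part. It rests on assumed arm differences, is negligible at 0.3 SD, and one covariate removes it. Reverse causation and common causes are not so easily removed.

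A reader might further infer that the 5-month data would establish mediation. They would not. The mediator is not randomized, and a persistent common cause still gave 12% to 66% false positives in the fully adjusted lagged model. Replacing the association tests with that model alone could also report a true early mechanism as absent.

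Finally, Hypothesis 3.2 drops the word *negative* from the cortisol slope and names pro-inflammatory cytokines instead of the ratio. A reader might take this as a reversed prediction. The direction is clear from Hypoth 2.2, Hypoth 2.3 and section 4.4, so it is a wording slip, but it leaves sign and variable open in a prespecified test.

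**Conclusion.** The concern holds in limited form. The plan calls cytokines, cortisol and psychosocial scores mediators and sets out a time order, but states only associations of change to 9 months and specifies no model that uses that order. On the natural reading, those associations cannot distinguish mediation from reverse causation or a common cause.

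For allocation alone, false rejection is 5.7%, 9.9% and 33.3% at assumed arm differences of 0.3, 0.5 and 0.8 SD with 124 completers, if the arms are pooled without an arm term. For reverse causation it is 64% to 89% pooled and 36% to 70% with arm adjusted, under the assumed simulation settings. None of these effect sizes comes from the documents.

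The documents do not support extending this to the randomized comparisons: the primary comparison and Hypoths 2.1, 2.2 and 3.1 do not depend on it. It is a change that should be made, not a threat to the main result.

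**What to change.** 1. In Hypoth 2.3 and 3.2, state the window on both sides and whether the sample is both arms or PP-T-CBSM only. Describe both hypotheses as associational.
2. Include arm and baseline values of mediator and outcome in every mechanism model that pools the arms.
3. Alongside the association tests, prespecify a time-ordered mediation analysis: arm to 5-month mediator to 9-month symptoms, with a bootstrap interval for the indirect effect.
4. Report it without and with adjustment for 5-month symptoms. The adjustment guards against symptoms having already moved the mediator by 5 months, but removes mediation completed by then; the two results should be read together.
5. Fit the reverse path (5-month symptoms to 9-month mediator) and a sensitivity analysis for mediator-outcome confounding.
6. Align Hypothesis 3.2 with Aim 2: the negative cortisol slope and the defined cytokine ratio.

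The cost is statistical wording and more analysis work; no visit, sample or questionnaire is added. Intervals will be wider than for simple associations, and a non-randomized mediator still gives no proof of causation.
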